Pre- and post-intervention patient-reported satisfaction and NSQIP outcomes. Management of pain will be assessed using elements of the Pain Treatment Satisfaction Scale (PTSS).¹⁴⁰ Previous work by Gupta et al suggests that, on average, 63% of patients provided assessments of pain control satisfaction in the upper quintile of a standardized 10-point satisfaction scale.¹⁴¹ Subsequent to the intervention, it is estimated that 73% of patients treated by PACTS-trained residents will report satisfaction in the uppermost PTSS quintile. We expect an 8% decrease in readmissions, from 23% to 15% post-intervention. Pre-post intervention differences in patient-reported satisfaction and NSQIP outcomes will be assessed using Chi-square, Fisher's exact tests, or t-tests as appropriate, and ordinal scale differences will be assessed using Chi-Square tests and ordered logistic regression, both without adjustment and controlled for patient-, clinician-, and facility-level factors. It is important to note that the patient groups represent independent samples, and these pre- and post-intervention measures are independent measures, not repeated measures (Table 8). To achieve this, we will recruit 100 patients per site for each data collection phase. Thus, we will collect 300 patients per site over the entire study (2,400 total), giving ample power for both patient and clinical outcomes.

Table 7. Sample Size Calculations

Example Measure	Proportional Difference to be Measured	Expected Minimum Number of Participants Per Group	Minimum Detectable Difference (80% power and $\alpha=0.05$)
Sample size/power calculations for repeated measures			
Within group resident knowledge/skills/attitudes	Pre- vs. Post-test proportion achieving "Adequate" vs. "sub-optimal" dichotomized assessments	Pre-intervention: 160 Post-intervention: 160 (Repeated Measures)	Pre-intervention: 50.0% Post-intervention: 61.0% Thus, we expect to be able to detect a proportional absolute difference of 11% for within-group assessments.
Sample size/power calculations for independent measures.			

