Between group resident knowledge/ Skills/attitudes	Post-test proportion in Early Group vs. Delayed Group achieving "adequate" vs. "sub-optimal" dichotomized assessments	Early Group: 159 Delayed Group: 159 (Independent Measures)	Change from 50% to 65.5% Assuming remains at 50% with no change from baseline assessment. Thus, we would be able to detect a 15% relative proportional difference between groups associated with exposure to PACTS training.
Patient-reported within and between-group differences			
Patient-reported outcomes	Pre- vs. Post-test proportion of patients reporting pain-satisfaction scores in the uppermost standardized quintile	Pre-intervention: 361 Post-intervention: 361 (Independent Measures)	Proportion of Patients with scores Pre-intervention: 63.0% Post-intervention: 73.0% Thus, we expect to be able to detect an absolute proportional difference of 10%.
Sample size/power calculation for NSQIP outcomes			
Readmissions	Pre- vs. Post-test proportion of patients readmitted	Pre-Intervention: 377 Post-intervention: 377	Proportion of Patients readmitted Pre-intervention: 23% Post-intervention: 15%

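### Aim 3 patient and NSQIP outcomes are specified and powered only as pre versus post, so a time trend shared by all sites enters the estimated PACTS effect

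*SAP*

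**What the plan says.** The SAP section on patient-reported satisfaction and NSQIP outcomes states one contrast: "Pre-post intervention differences in patient-reported satisfaction and NSQIP outcomes will be assessed using Chi-square", Fisher's exact or t-tests, with ordered logistic regression for ordinal scales. Models are to be run "both without adjustment and controlled for patient-, clinician-, and facility-level factors". No arm, period or arm-by-period term is named, and the section does not say how the two arms are combined.

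The two Aim 3 rows of Table 7 describe the quantity to be measured as "Pre- vs. Post-test proportion of patients reporting pain-satisfaction scores in the uppermost standardized quintile" (63% to 73%, 361 per group) and "Pre- vs. Post-test proportion of patients readmitted" (23% to 15%, 377 per group).

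On enrolment, "we will recruit 100 patients per site for each data collection phase", which makes 300 per site and 2,400 in all, described as "giving ample power for both patient and clinical outcomes".

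A between-group comparison is mentioned in three general places: the protocol's Research Design and Methods, the opening of the SAP, and the Table 7 heading above the patient-reported row. Only the resident outcomes get an Early-versus-Delayed test (SAP, Between-group differences) together with an effect and a sample size (Table 7: 50% versus 65.5%, 159 per group).

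**The concern.** Eight sites are randomised to early or delayed training, yet the one test written out for Hypothesis 3 compares patients before and after training. Anything that changes outcomes at all sites over the same months is then counted as a PACTS effect. A favourable trend could appear to support Hypothesis 3 when PACTS does nothing; an unfavourable one could hide a real benefit. The adjustment set has no period term, so it could remove at most the part of a trend that runs through measured case mix. Drift is plausible here: the protocol itself cites the pandemic and a heightened focus on equity in medicine during the trial (Resident Curriculum Impact Focus Groups).

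**Working it through.** **1. The plan's own figures.** Inputs from Table 7: 80% power, alpha 0.05 (two-sided reproduces the figures).

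n = [1.960·√(2p̄(1−p̄)) + 0.842·√(p₁(1−p₁)+p₂(1−p₂))]² / (p₁−p₂)²

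- Satisfaction, 0.63 vs 0.73: 340.4, so 341. The continuity correction (n/4)(1+√(1+4/(n·0.10)))² gives 360.1, so **361**, as stated.
- Readmission, 0.23 vs 0.15: 376.3, so **377**, as stated (401 with the correction).

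Both are plain two-sample pre-versus-post calculations, with no arm, period or clustering.

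**2. Patients per cell.** 300/100 = 3 phases per site, and 8 × 300 = 2,400. With half the sites in each arm, each arm has 4 × 100 = 400 patients per phase. Delayed sites are trained the following year, so their patients in both Year 2 phases would be concurrent and unexposed. This is inferred from the arithmetic and the SAP's three time points. The protocol describes only windows before and after the intervention (Research Design and Methods, Patients; Equitable Selection of Subjects, Patients).

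**3. How much of a shared trend enters.** Let p₁, p₂, p₃ be the phase means with no PACTS effect.

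- Within one arm, before versus after: all of the change.
- Pooled by exposure, no period term. Exposed mean = (p₂+2p₃)/3 (Early phases 2 and 3, Delayed phase 3). Unexposed mean = (2p₁+p₂)/3. The difference is **2(p₃−p₁)/3**, whatever the shape of the drift.
- The same with site effects. Exposure centred within site is (−2/3, 1/3, 1/3) for Early and (−1/3, −1/3, 2/3) for Delayed. Least squares gives (p₃−p₁)/(4/3) = **0.75(p₃−p₁)**.

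**4. Chance of p<0.05 with no PACTS effect** (two-sided pooled test, before clustering; drift sizes assumed):

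| Outcome, shared drift | Within arm, 400 vs 400 | Pooled by exposure, 1,200 vs 1,200 (same total drift over the study) |
|---|---|---|
| Satisfaction, +3 points | 14% | 17–18% |
| Satisfaction, +5 points | 32% | 40–41% |
| Readmission, −3 points | 18% | 22–23% |
| Readmission, −4 points | 28% | 35–37% |

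The ranges cover early, late and linear drift. Pooling lets in less of the trend, but the larger n makes it significant more often. Under the same drift, a post-phase Early-versus-Delayed test and a year-1 difference-in-differences both stay at 5%.

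**5. Power of the randomised contrasts.** The SAP's 10- and 8-point effects are assumed, with Delayed sites staying at the pre rate (a = pre, b = post).

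- Difference-in-differences: SE = √([3a(1−a)+b(1−b)]/n). At n = 400 per cell, √(0.8964/400) = 0.0473 and √(0.6588/400) = 0.0406. Power = Φ(effect/SE − 1.96) = 56% and 50%.
- Three-phase least squares with site and period effects, 100 per site-phase: SE 0.0402 and 0.0338, power 70% and 66%.
- Post-phase Early versus Delayed, 400 per arm: 86% and 82%.

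Power, satisfaction/readmission, before clustering:

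| Total patients | Difference-in-differences | Three-phase | Post-phase |
|---|---|---|---|
| 2,400 | 56%/50% | 70%/66% | 86%/82% |
| 2,760 | 62%/56% | 76%/72% | 90%/87% |
| 3,105 (even spread assumed) | 67%/61% | 81%/77% | 93%/91% |

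With an assumed site-level SD t, the variance grows by t² (difference-in-differences), t²/2 (post-phase) or t² per cell mean (three-phase). For t of 2 to 3 points at 2,400, satisfaction and readmission power are 49–43% and 42–35%, 63–55% and 56–47%, and 80–73% and 73–63%, in the table's column order. Normal critical values are used, so corrections for 8 sites would lower these further.

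**The case against.** The strongest reply is that this is under-specification, not a decision to ignore the arms. The opening of the SAP covers the whole plan, the protocol lists patient outcomes under the randomised design, and the Table 7 heading mentions between-group differences. The SAP also uses pre-versus-post wording for a resident comparison that is between arms. A between-group analysis may well be intended. What stands is that intent supplies no test, effect or sample size, and the only row under that heading is pre versus post. The SAP also cites a Table 8, which is not in the available text; the sentence citing it concerns the independence of the pre and post samples.

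Four further points have some weight:

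- Pooling by exposure is one reading of the plan, not something it states, and it gives partial concurrent control. It still admits two-thirds to three-quarters of the trend.
- Every drift size is assumed, so the rejection rates illustrate direction and scale only.
- The 5% rate for the alternatives holds only without site variation. An uncorrected post-phase test with a site SD of 2, 3 or 5 points would reject about 7%, 10% or 17% of the time for satisfaction and 8%, 11% or 21% for readmission. That is why the replacement must allow for clustering.
- Since the needed patients appear to be planned already, the gap could be called one of SAP text. But the text as it stands prescribes a test that confounds PACTS with time.

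**Conclusion.** The concern holds, and it must be fixed before Aim 3 is analysed. The stated pre-post test cannot separate PACTS from calendar time, and the claim of sufficient power was shown only for that test. The reading of the text and the reproduction of 361 and 377 rest on no assumption. The false-positive figures (14% to 32% within an arm) rest on assumed drifts of 3 to 5 points and no clustering. At 2,400 patients the contrasts based on change fall below 80% power even before clustering. The post-phase contrast does not, but it carries lasting site differences: 55%/43% if the site SD were 5 points.

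**What to change.** 1. Confirm in the SAP that Delayed-site patients are enrolled in both Year 2 phases, and reconcile this with the protocol's pre and post windows.
2. Make a randomised Early-versus-Delayed contrast the main Aim 3 analysis: a model with site and period effects, a PACTS-exposed indicator, the covariates already listed, and a clustering method suited to 8 sites. State the retention assumption if the third phase is used.
3. A post-phase Early-versus-Delayed comparison, as already planned for residents, also removes a shared trend but has no baseline control with only 8 sites. Say which contrast is chosen and why.
4. Keep the pre-post tests as descriptive.
5. Restate the patient rows of Table 7 and the power claim for the chosen contrast and one reconciled enrolment. The documents give 2,400 (SAP; protocol enrolment table) and 3,105 (protocol, Equitable Selection of Subjects and Patient Recruitment). The protocol's 345 per site gives 345 × 8 = 2,760, while 3,105 = 345 × 9.
6. If Delayed sites enrol no concurrent patients, state that Aim 3 cannot separate PACTS from time.

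Cost: SAP text, model and power rows. No extra patients are needed to run the analysis if the three-phase scheme goes ahead, but stated power falls. Reaching 80% with a year-1 difference-in-differences would take 704 per cell (4 × 704 = 2,816) for satisfaction and 808 per cell (4 × 808 = 3,232) for readmission, before clustering.

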In anticipation of this protocol, we have pilot-tested the curriculum at three affiliated institutions with general surgery residents at varying levels of training. Focus group data was collected to garner feedback on the effectiveness and feasibility of the curriculum. **The purpose of the current protocol is to implement the curriculum across eight institutions and measure resident-level competency outcomes, as well as patient-reported and clinical outcomes, following this training.**

RESEARCH DESIGN AND METHODS

Briefly describe study design and anticipated enrollment, i.e., number of subjects to be enrolled by researchers study-wide and by Partners researchers. Provide a brief summary of the eligibility criteria (for example, age range, gender, medical condition). Include any local site restrictions, for example, "Enrollment at Partners will be limited to adults although the sponsor's protocol is open to both children and adults."

We will conduct a cross-over, cluster-randomized trial at 8 academic medical centers (AMCs) to capture the effect of PACTS on: 1) resident knowledge and attitudes regarding cross-cultural health care [Specific Aim (SA)1], 2) interpersonal and communication skills in simulated patient-clinician encounters [SA2], and 3) patient-reported satisfaction with resident physicians involved in their care, and clinical outcomes [SA3]. Sites will be assigned to an early intervention/retention assessment group or a control group with delayed intervention for examination of the effectiveness of the intervention as well as learner retention. After cluster-randomization, we will assess the residents' knowledge, attitudes, and skills prior to and after the PACTS curriculum at half the sites (Early Intervention/Retention Group). We plan to conduct follow-up testing after one year to evaluate learner retention.

At the other sites (Delayed Intervention Group), we will conduct baseline testing prior to the standard residency curriculum, and administer the PACTS curriculum the following year. This study design will enable us to examine both between- and within-group differences based on curriculum exposure in intervention year 1 as well as within-group differences for the Delayed Intervention Group at the end of year 2. Further, we will also be able to test post-exposure effect retention in the Early Intervention Group at the end of year 2.

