All general surgery residents will receive the educational curriculum; each site's Program Director (PD) has agreed to schedule PACTS training during compulsory didactic sessions, when residents are free from clinical duties. However, participation in study assessments (OSCEs and knowledge-testing) is voluntary and will not impact residents' performance in their program. Final analyses will include enrolled residents regardless of their attendance in live modules, reflecting an "intention-to-treat" analysis approach. This will more accurately demonstrate the "real world" benefit of PACTS, as not all residents may be able or willing to attend all live sessions. Based on the size of the residency programs, which ranges between 46 and 72 residents, and the away rotation schedules, we expect to enroll 200 residents per arm for analysis (an average of 50 residents per site).

Patient Recruitment

At the onset of clinical rotations, the Program Manager will contact surgical residency Program Coordinators to attain general surgery resident rotation schedules. The Program Manager will identify the dates and times of resident study participants' rotations. On these dates and times, Research Assistants working under the supervision of the Program Manager will verify that the resident is on rotation and use the EHR at the surgical service site to

randomly select at least two eligible patients from the EHR. First, the RA will approach the patients' nurse and ask whether the nurse might have a concern regarding the selected patients' cognitive status. If the nurse has no concerns, the nurse will be asked to introduce study staff to the patient. Staff will provide an information sheet, describe the study, and ask them to identify a resident participating in the PACTS trial who they recall interacting with. The RA will explain the study and provide the patient with a copy of the Patient Information Sheet and survey, which will be administered via tablet or laptop computer to access the survey in the Partners-hosted REDCap database. Completion of the English or Spanish language survey will indicate consent to participate in the study and the patient will be enrolled.

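### The Aim 3 patient comparisons ignore clustering by site: pre-post tests are sound only if site effects stay stable between phases, and any Early-versus-Delayed patient test is anti-conservative and undersized

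*SAP*

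**What the plan says.** The Protocol (Research Design and Methods) describes the design as follows: "We will conduct a cross-over, cluster-randomized trial at 8 academic medical centers (AMCs". Patients are identified from the lists of enrolled residents during the pre and post windows (Equitable Selection of Subjects). For each resident on rotation, research assistants will "randomly select at least two eligible patients from the EHR" (Recruitment Procedures, Patient Recruitment).

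The SAP (paragraph on patient-reported satisfaction and NSQIP outcomes) says that "the patient groups represent independent samples, and these pre- and post-intervention measures are independent measures, not repeated measures", and that "we will recruit 100 patients per site for each data collection phase". Over three phases this gives 300 per site and 2,400 in total. The tests named are chi-square, Fisher's exact or t-tests. Ordinal scales get chi-square and ordered logistic regression, with and without patient, clinician and facility covariates.

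Table 7 sizes pain satisfaction as "Pre-intervention: 361 Post-intervention: 361 (Independent Measures") for "Pre-intervention: 63.0% Post-intervention: 73.0"%, under a row heading that covers both within-group and between-group patient differences. Readmissions get 377 per group for "Pre-intervention: 23% Post-intervention: 15"%, labelled pre versus post only.

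Neither document names an ICC, design effect, random effect, GEE or cluster-robust variance for the patient outcomes.

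**The concern.** Sampling different patients in each phase means that no patient is measured twice. It does not make patients of the same resident and site independent of one another. PACTS is delivered to a whole site at once, so anything else that moves that site between phases (staffing, pain protocols, case mix) is shared by all 100 patients in a site-phase. The plain tests count each of those patients as separate evidence on the change.

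Aim 3 carries the trial's claim of benefit to patients. If sites drift differently between phases, that drift will be declared a PACTS effect more often than 5% of the time, and confidence intervals will be too narrow. In a comparison of Early with Delayed sites, ordinary differences between hospitals act in the same way.

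**Working it through.** **Inputs.** From the SAP: 63% vs 73%, 23% vs 15%, 80% power, alpha 0.05 (sidedness not stated; two-sided reproduces the figures), and m = 100 patients per site-phase. From the Protocol: 8 sites, so 400 patients per arm and 800 overall in each phase. Assumed, because the documents give neither: within-site ICC 0.01, 0.02 or 0.05, and CAC (the correlation of a site's effect between phases) 1, 0.8 or 0.5.

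**Table 7 first.** The two-proportion formula is n = [1.96√(2p̄q̄) + 0.842√(p1q1 + p2q2)]² / (p1 − p2)².
- 63% vs 73%: 340.4, rounded up to 341; with continuity correction 360.1, rounded up to 361 (stated 361).
- 23% vs 15%: 376.3, rounded up to 377 (stated 377); with continuity correction 401.

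Both match exactly under independence, one with and one without continuity correction. Neither leaves room for clustering.

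**Design effects.**
- Pre vs post in the same sites: DE = 1 + (m − 1)ICC − m·ICC·CAC.
- Between arms: DE = 1 + (m − 1)ICC.
- True type I error of the plain test: 2[1 − Φ(1.96/√DE)].
- Number needed: Table 7's figure × DE.

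Example, ICC 0.05 and CAC 0.8: DE = 1 + 4.95 − 4.00 = 1.95; 1.96/√1.95 = 1.40, which gives 16%; 361 × 1.95 = 704.

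| Comparison | DE at ICC 0.01 / 0.02 / 0.05 | Type I error | Needed, satisfaction | Needed, readmission |
|---|---|---|---|---|
| Pre-post, CAC 1 | 0.99 / 0.98 / 0.95 | 4.9 / 4.8 / 4.4% | 358 / 354 / 343 | 374 / 370 / 359 |
| Pre-post, CAC 0.8 | 1.19 / 1.38 / 1.95 | 7 / 10 / 16% | 430 / 499 / 704 | 449 / 521 / 736 |
| Pre-post, CAC 0.5 | 1.49 / 1.98 / 3.45 | 11 / 16 / 29% | 538 / 715 / 1,246 | 562 / 747 / 1,301 |
| Early vs Delayed | 1.99 / 2.98 / 5.95 | 16 / 26 / 42% | 719 / 1,076 / 2,148 | not a labelled comparison |

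A simulation of the plain test (40,000 runs per setting) agrees. For satisfaction at CAC 0.8 with 4 sites it gives 7.2% at ICC 0.01 and 16.3% at ICC 0.05. Between arms at ICC 0.05 it gives 42.1%.

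**Margin in planned recruitment.** One arm: 400/361 = 1.11 and 400/377 = 1.06. All 8 sites: 800/361 = 2.22 and 800/377 = 2.12. A single arm therefore cannot absorb even DE 1.19. The pooled 8 sites absorb a DE of about 2.1 to 2.2 as far as power goes, but extra patients do not correct the type I error of the plain test.

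**Power of a valid site-level test.** This is a t-test on k site differences with k − 1 degrees of freedom and SE = √[(p1q1 + p2q2)·DE/(100k)]. For satisfaction at ICC 0.01, CAC 1 and k = 4: SE = √(0.4302 × 0.99/400) = 0.0326, so the effect is 3.06 SE against a critical value of 3.18, and power is 55%. Over both outcomes and ICC 0.01 to 0.05:
- 4 sites: 51-56% at CAC 1 and 31-48% at CAC 0.8.
- 8 sites: 94-96% at CAC 1 and 71-92% at CAC 0.8.

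**The case against.** The strongest reply is that shared sites help a pre-post contrast. Each site acts as its own control, so stable differences between hospitals cancel. At CAC 1 the plain tests are slightly conservative, and 361 and 377 stand. This is correct. A reader might infer from the nesting alone that the Aim 3 error rate and Table 7 fail outright, and the documents do not support that. Only variation between phases within a site does the damage, and its size is unknown. Nor do the documents say that the same residents appear in every phase. Residents are PGY 1-5 and the phases span two study years, so some turnover is likely.

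Table 7's numbers are labelled as minimums, and 800 patients per phase over 8 sites exceed them. That stands for power when all sites are pooled. It does not stand for a single arm or for type I error.

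The low 4-site power should not be blamed on clustering alone. It is already 51-56% at CAC 1, against 86% (satisfaction) and 82% (readmission) for a plain test on 400 per phase treated as independent. Most of that loss comes from having 3 degrees of freedom.

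The adjusted ordinal models might absorb some stable site differences. Ordinary covariates do not model site-by-phase variation, and the text ties adjustment to ordinal outcomes.

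The between-arm figures rest on one row heading in Table 7. The row itself and the SAP text describe pre versus post, so those figures apply only if such a comparison is made.

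Two inputs are unsettled. The Protocol gives about 345 patients per site where the SAP gives 300. It also describes NSQIP outcomes for all patients in Aim 3 but for each patient participant under study procedures. The value m = 100 follows the SAP.

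**Conclusion.** The concern holds in conditional form. The plan has no cluster-aware analysis for Aim 3, and Table 7 has no design effect. The claim of independence is right only in the narrow sense that no patient is measured twice.

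Under the assumed ICC range of 0.01 to 0.05, the pre-post tests are valid or slightly conservative if site effects are stable. They are anti-conservative if sites change differently between phases: about 7-16% at CAC 0.8 and 11-29% at CAC 0.5. At CAC 0.8 the need is 430-704 per group for satisfaction and 449-736 for readmission. The SAP neither states nor justifies stable site effects, and the Protocol itself records COVID-19 changes during the trial.

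For an Early-versus-Delayed patient comparison no value of CAC helps, because the arms share no sites. Type I error is about 16-42%, and 400 per arm falls well short of 719 to 2,148.

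**What to change.** In the SAP:

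1. Replace the independence statement with one saying that different patients are sampled in each phase from the same sites.
2. Make the main analysis of each patient-reported and NSQIP outcome a mixed model (logistic, ordinal or linear) with effects for site, site-by-phase and, where patient records are linked to a resident, resident, with a small-sample correction. A site-level analysis of site-phase summaries is an acceptable alternative. Keep chi-square, Fisher and t-tests as description.
3. Restate the patient and readmission rows of Table 7 over a stated ICC and CAC range. Say for each row whether it uses 4 or 8 sites and whether it is pre-post or Early versus Delayed. Report the detectable difference at the planned 100 per site per phase, with no extra patients.

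The cost is SAP text, some added analysis work, wider intervals and a less favourable stated power, most visibly wherever only 4 sites are used.

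The limit should be stated too: site-by-phase effects do not protect a pre-post comparison against a time trend common to all sites. In a simulation with 8 sites, ICC 0.01, CAC 0.8 and no PACTS effect, a paired site-level test rejected about 18% of the time under an assumed shared shift of 3 points, and about 40% under 5 points.

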3. Aim 3: Assess effectiveness of PACTS on improving clinical outcomes and patient-reported outcomes. We will survey patients cared for by residents enrolled in the study on: (1) satisfaction with pain management, (2) physician communication, (3) trust and (4) comprehension of informed consent. In addition, we will use data from the National Surgical Quality Improvement Program (NSQIP) to measure surgical complications, length of stay, 30-day mortality, morbidity, and readmissions for all patients.

Hypothesis 3: Patients cared for by residents who have completed PACTS will exhibit better clinical and patient-reported outcomes.

BACKGROUND AND SIGNIFICANCE

Provide a brief paragraph summarizing prior experience important for understanding the proposed study and procedures.

Minority patients experience worse overall health outcomes, and these disparities are especially apparent in the costly, high-risk specialty of surgical care. To address this, the National Institute on Minority Health and Health Disparities (NIMHD) collaborated with the American College of Surgeons (ACS) to establish research priorities for surgical disparities. One of the top priorities was to evaluate the effect of improvement in culturally dexterous care on surgical outcomes for patients from disparity populations. Adverse outcomes for minority patients, including patients with limited English proficiency, have been demonstrated because of poor patient-provider communication. We propose that such deficiencies in communication contribute to treatment errors, inadequate pain management, less patient-centered care, decreased adherence to treatment plans, and worse overall clinical outcomes. Additionally, studies have illustrated the preponderance of pro-White implicit biases, which are unconscious, automated preferences that individuals may not even be aware of, among surgeons.

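### The SAP claims ample power for clinical outcomes in general, but shows it only for readmission; the claim is undemonstrated for the other clinical outcomes and fails for rare ones

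*SAP*

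**What the plan says.** The SAP section on patient-reported satisfaction and NSQIP outcomes sets the patient sample: "we will recruit 100 patients per site for each data collection phase". It then concludes: "Thus, we will collect 300 patients per site over the entire study (2,400 total), giving ample power for both patient and clinical outcomes". The clinical effect it names is on readmission: "We expect an 8% decrease in readmissions, from 23% to 15% post-intervention".

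Table 7 has two patient-level rows. Pain satisfaction (63% to 73%) has "Pre-intervention: 361 Post-intervention: 361 (Independent Measures"). Readmission has "Pre-Intervention: 377 Post-intervention: 377". The column heading sets 80% power and alpha 0.05.

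The clinical outcomes planned are wider than that. Aim 3 in the protocol's Specific Aims uses NSQIP data "to measure surgical complications, length of stay, 30-day mortality, morbidity, and readmissions for all patients". The Patients part of Research Design and Methods adds unplanned reoperations. For none of these except readmission does either document give an expected rate, a standard deviation, a target difference or a power figure, and no clinical outcome is named as primary.

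**The concern.** Power for a binary outcome depends heavily on how common the event is. Readmission is sized at 23%, a frequent event, so an 8-point fall is available to be detected. The same relative benefit on a rarer event is a much smaller absolute difference, and the same number of patients may say little about it. A general statement of ample power, supported by one frequent outcome, therefore covers outcomes for which nothing has been calculated.

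What is at stake is interpretation. Hypothesis 3 predicts better clinical outcomes. If mortality or reoperation shows no significant difference, a plan that already records ample power invites the reading that a worthwhile effect was ruled out. The documents do not say that such a result will be read that way, but nothing in them guards against it.

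**Working it through.** **Inputs.** Readmission 23% to 15%, 377 per group, 80% power, alpha 0.05 (SAP Table 7). Sidedness is not stated; two-sided is assumed and is checked in step 1. There are 8 sites, half early and half delayed (protocol, Research Design and Methods), 100 patients per site per phase, and three phases (SAP). Base rates for the other outcomes are assumptions.

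**Step 1: reproduce the plan's figure.** With p̄ = (p1 + p2)/2, A = √[2p̄(1 − p̄)] and B = √[p1(1 − p1) + p2(1 − p2)]:

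n per group = (1.960·A + 0.8416·B)² / (p1 − p2)²

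For 0.23 and 0.15, p̄ = 0.19, A = 0.5548 and B = 0.5519, so n = (1.0874 + 0.4645)² / 0.0064 = 376.3, that is 377. This matches exactly. A one-sided test would give 297, so two-sided is right. The pain row's 361 needs a continuity correction (341 without it), so the two rows use different variants. That does not affect what follows.

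**Step 2: the effect size.** 8/23 = 34.8% relative reduction; relative risk 15/23 = 0.652.

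**Step 3: group sizes that 2,400 patients can supply.**
- One arm in one phase: 4 × 100 = 400.
- All sites in one phase: 8 × 100 = 800.
- All exposed against all unexposed: exposed are the early arm at both post-intervention phases and the delayed arm at the last, 3 × 400 = 1,200; unexposed are the remaining 1,200. The SAP does not name this contrast. It is the most favourable split of 2,400.

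**Step 4: same relative cut, other base rates.** Power = Φ[((p1 − p2)√n − 1.960·A)/B]. Worked example at 5% and n = 1,200: p2 = 0.05 × 15/23 = 0.0326, difference 0.01739, A = 0.28142, B = 0.28115. Then (0.01739 × 34.641 − 1.960 × 0.28142)/0.28115 = 0.181, and Φ(0.181) = 57%.

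| Base rate | Rate after cut | n per group for 80% | Power at 400 | at 800 | at 1,200 |
|---|---|---|---|---|---|
| 23% (readmission) | 15.0% | 377 | 82% | 98% | >99% |
| 15% (assumed) | 9.8% | 625 | 61% | 89% | 97% |
| 10% (assumed) | 6.5% | 983 | 43% | 72% | 87% |
| 5% (assumed) | 3.3% | 2,055 | 23% | 42% | 57% |
| 2% (assumed) | 1.3% | 5,270 | 12% | 19% | 27% |

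Solving for the lowest base rate with 80% power at this relative cut gives 21.9% at 400 per group, 12.1% at 800 and 8.3% at 1,200.

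**Step 5: a larger sample.** The protocol elsewhere gives 3,105 patients. Split in half (about 1,552 per group), the 80% threshold falls to a base rate of 6.5%; power is 68% at 5% and 33% at 2%.

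**Step 6: length of stay.** It is continuous, and no SD or target difference is given, so no power can be computed.

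**The case against.** A reader might infer that the trial cannot have adequate power for complications, morbidity or reoperation. The documents do not support that. They give no base rates, and if such an outcome runs at 8.3% or more, the 1,200 against 1,200 comparison reaches 80% power for the same relative cut; at 15%, even 800 per group gives 89%. For these outcomes the fair statement is that power has not been shown.

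In the plan's defence, Table 7 heads its first column as example measures, readmission is the only NSQIP outcome the SAP discusses by name, and the longer list comes from a protocol dated 2020 against a 2017 SAP. Sizing on one example outcome is common practice, and no arithmetic in the readmission row is wrong. All of that stands. It does not rescue the sentence, which speaks of clinical outcomes without limit in a section that plans tests on NSQIP outcomes in the plural. An example at 23% supports outcomes of similar frequency, not rare ones.

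The clinical sample may also be larger than 2,400. Aim 3 speaks of NSQIP data for all patients, whereas the procedures text ties the outcomes to each patient participant. If a full registry sample were meant, power could be higher. But the SAP derives its claim from the 2,400 recruited patients, and no registry sample size is given.

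**Conclusion.** The power claim is supported for one clinical outcome only: readmission, for an 8-point fall from 23%, with patients treated as independent. For complications, morbidity and reoperation it is not demonstrated; whether it holds depends on base rates the documents omit and on which comparison is used. For any outcome at about 5% or below it does not hold at the relative effect the plan expects for readmission: power is at most 57% on the best split of 2,400 patients and 27% at a 2% rate. Thirty-day mortality falls in this group if it is that rare, which is an assumption. Length of stay cannot be judged.

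These figures rest on a two-sided 5% test, the normal approximation, a 34.8% relative cut carried over to other outcomes, and no clustering. The last is generous to the plan. With an assumed intracluster correlation of 0.01 and 100 patients per site per phase, the design effect is 1 + 99 × 0.01 = 1.99, and readmission power at 400 per group falls from 82% to 53%, giving no credit for comparing within sites. The conclusion does not depend on this, but the two sized rows should not be restated as if clustering had been allowed for.

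**What to change.** Replace the general sentence with one limited to what was calculated: 80% power for a 10-point difference in pain satisfaction (361 per group) and an 8-point difference in readmission (377 per group), each treating patients as independent and making no allowance for clustering by site or resident.

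For complications, morbidity, reoperation and 30-day mortality, do one of two things:
- state an assumed base rate, the comparison and its group sizes, and the difference detectable with 80% power. For example, at an assumed 5% rate that is a fall to about 2.8% with 1,200 per group, 2.4% with 800 or 1.5% with 400; or
- label them exploratory and report estimates with confidence intervals.

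In either case, say that a non-significant test will not be taken as evidence of no effect. For length of stay, give an SD and a detectable difference or treat it as exploratory. State also whether the NSQIP outcomes cover only surveyed patients or all patients, since that sets the sample.

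The cost is SAP wording only, with no extra patients or procedures. The drawback is that the stated sensitivity of the trial becomes less favourable.
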